PROTOCOL CAPTRANE

Multicenter, open-label, randomized study comparing topical treatment with 8% capsaicin patch (Qutenza) to oral pregabalin in the early management of intercostobrachial neuralgia (ICBN) following primary surgery for breast cancer.

A) CLINICAL TRIAL IDENTIFICATION

STUDY TITLE	Multicenter, open-label, randomized study comparing topical treatment with 8% capsaicin patch (Qutenza) to oral pregabalin in the early management of intercostobrachial neuralgia (ICBN) following primary surgery for breast cancer.
SHORT TITLE	CAPTRANE
INVESTIGATOR COORDINATOR	[name]
EUDRACT	2018-003559-39
REF ANSM	MEDAECNAT-2018-20-00041
ETHICS COMMITTEE NAME	CPP SUD MEDITERRANEE IV (MONTPELLIER)
REF ETHICS COMMITTEE	18.11.04
N° CLINICAL TRIAL.GOV	NCT03794388

B) STUDY BACKGROUND

Epidemiology of Breast Cancer

Breast cancer is the most common cancer in women in both the European Union and the United States. In France, 54,000 new cases of breast cancer in women were recorded in 2015. Although its incidence has been decreasing over the past decade, breast cancer remains the most frequent malignancy, ahead of colorectal and lung cancer (2). This cancer is far less common in men.

Breast cancer mortality has been declining since the late 1990s. According to data from the French National Cancer Institute, the five- and ten-year net survival rates are high, at 86% and 76% respectively for individuals diagnosed between 1989 and 2004 (2). Breast cancer has therefore become a chronic disease, and patients must learn to live with it as well as with the adverse effects linked either to the disease itself or to the treatments administered.

As highlighted by the third Cancer Plan (Action 8.3: "Improve the management of physical sequelae of cancer treatments") (3), in continuity with the previous Cancer Plan and the fourth National Pain Management Plan (4), pain is a major criterion impacting the quality of life of patients treated for breast cancer.

Neuropathic Pain in Patients with Breast Cancer

Definitions

Neuropathic pain was defined in 2011 by the International Association for the Study of Pain (IASP) as the direct consequence of a lesion or disease affecting the somatosensory system (5). Nociceptive pain corresponds to a normal—although variably adapted—response of the physiological "alarm system" triggered by a lesion threatening tissue integrity. In contrast, "neuropathic pain is always pathological, as it reflects disturbances and dysfunctions of physiological nociceptive systems" (6). Pain is described as mixed when it includes both neuropathic pain and pain related to nociceptive overload, which is often the case in tumor progression (5).

Etiology of Neuropathic Pain in Patients With Breast Cancer

Breast cancer treatments are divided into locoregional treatments—surgery and radiotherapy—and systemic treatments such as chemotherapy (including targeted therapies) and hormone therapy administered either as adjuvant or neoadjuvant therapy.

Among these treatments, only hormone therapy does not directly induce neuropathic pain, although prolonged administration may lead to nociceptive pain of musculoskeletal origin (7). Chemotherapy can also cause neuropathic pain as part of a sensorimotor peripheral neuropathy, which most often improves after discontinuation of treatment (5). Adjuvant radiotherapy may complement surgery. Irradiation may target the breast, the chest wall in cases of total mastectomy, and possibly regional lymph nodes. The risk of radiation-induced plexopathy exists, although it is less frequent with current radiotherapy techniques (8).

Surgery is often the first treatment for breast cancer. It may be breast-conserving, through partial mastectomy (lumpectomy or quadrantectomy), or non-conserving, through total mastectomy. These procedures are frequently combined with axillary surgery: either axillary lymph node dissection involving removal of 8–10 lymph nodes, or sentinel lymph node biopsy, which consists of identifying and excising the first lymph node(s) draining the breast. Axillary dissection is performed only if the sentinel lymph node is metastatic (9).

Intercostobrachial Neuralgia (ICBN)

Intercostobrachial neuralgia (ICBN), also referred to as Intercostobrachial Neuralgia (10) or Post-Mastectomy Pain Syndrome (PMPS), was first described by Wood in 1978 as “a chronic pain that begins immediately or soon after a mastectomy or lumpectomy and affects the anterior chest, axilla, and/or upper half of the arm.”

These postsurgical pains are related to injury of nerves within the breast region. In particular, the intercostobrachial nerve may be transected, stretched, or compressed during surgery. However, literature reports indicate that nerve injury does not always result in pain.

Furthermore, axillary dissection may lead to upper-limb lymphedema, which can maintain or exacerbate pre-existing intercostobrachial neuralgia. Breast-conserving surgery appears to be associated with a lower risk of ICBN than mastectomy combined with axillary dissection. Postoperative complications, such as hematoma or infection, also seem to increase the incidence of ICBN. Overall prevalence ranges between 32% and 58%, though it varies widely across studies and depends on the pain assessment method used (8).

[figure not shown]

Figure 1: Innervation of the breast and location of nerves at risk during surgery (Reg Anesth Pain Med, 2014, Wijayasinghe N. et al.)

**Assessment of Neuropathic Pain**

Postoperative neuropathic pain in breast cancer patients is underdiagnosed, both in primary care and in specialized settings. This diagnostic difficulty is attributed to challenges in early recognition and clinical identification of neuropathic pain (11, 12). Diagnosis is based on clinical history and physical examination; no additional tests are required (12).

History-taking helps identify pain characteristics (paresthesia, burning sensations...). Neurological examination should assess for signs suggestive of involvement in a neuroanatomically plausible territory of the peripheral nervous system. This includes negative sensory signs (sensory deficits) as well as positive signs such as hyperalgesia or mechanical allodynia.

Several screening tools can detect neuropathic pain. In France, the most commonly used is the DN4 questionnaire (Douleur Neuropathique en 4 questions), consisting of 10 items covering pain descriptors. It has excellent sensitivity (82.9%) and specificity (90%) (13). The S-LANSS (Self-report Leeds Assessment of Neuropathic Symptoms) is also useful, with sensitivity of 85% and specificity of 80% (14). Other tools (Neuropathic Pain Questionnaire, ID Pain, PainDETECT, Standardized Evaluation) are less convenient for routine practice. The DN4 is currently recognized as the most specific and sensitive scale (8).

Patients do not always report these symptoms. They may fail to associate their pain with the surgery when pain appears weeks or months after the procedure, or they may consider it normal to experience pain at the surgical site (11). These diagnostic challenges delay adequate analgesic management, thereby promoting chronic neuropathic pain.

Treatment of Neuropathic Pain

There is no consensus regarding the management of neuropathic pain in cancer patients. Recommendations for non-cancer-related neuropathic pain are currently applied by extrapolation (11).

Systemic Treatments

Neuropathic pain responds poorly to conventional analgesics such as paracetamol or non-steroidal anti-inflammatory drugs. Three major therapeutic classes are indicated: tricyclic antidepressants (amitriptyline, imipramine, clomipramine), antiepileptics (pregabalin, gabapentin), and opioids.

Systemic analgesics may be poorly tolerated due to side effects that can compound those of cancer treatments. For example, breast cancer patients receiving hormone therapy may experience menopausal-like symptoms including weight gain. Tricyclic antidepressants and pregabalin can also cause weight gain. According to the 2007 French Health Authority report, weight gain affects 3.5% of patients receiving pregabalin at 600 mg/day (15). Adverse effects from hormone therapy and neuropathic pain management may therefore add up and should be considered when developing the therapeutic strategy.

According to good practice recommendations from the French Society for the Study and Treatment of Pain, the choice of treatment depends on clinical context, comorbidities, safety profile, and cost (lower for tricyclic antidepressants) (16).

Topical Treatments

Systemic treatments may be combined with topical therapies such as lidocaine or capsaicin patches.

5% Lidocaine Plasters (VERSATIS®)

Lidocaine 5% plasters (VERSATIS®) received a European marketing authorization in 2007 for the treatment of post-herpetic neuralgia in patients with mechanical allodynia. The topical formulation is useful when systemic treatments are contraindicated. Tolerance is excellent, with minimal adverse effects compared to systemic treatments (17).

8% Capsaicin Patches (QUTENZA®)

Capsaicin 8% patches (QUTENZA®), marketed in France since 2011, are an innovative treatment for localized postsurgical neuropathic pain. Capsaicin is an agonist of the transient receptor potential vanilloid 1 (TRPV1) channel. It is indicated for the treatment of peripheral neuropathic pain in adults, alone or in combination with

other analgesics (1). The patch is applied to the most painful intact skin areas for 60–90 minutes, up to four patches simultaneously. Applications may be repeated every 90 days if needed. Application must be performed by a physician or healthcare professional in a hospital setting. Its major advantage lies in its low rate of adverse effects (10%), mostly mild erythema, burning sensations, or pruritus at the application site (1). Furthermore, the effect is long-lasting. Recent studies have demonstrated the superiority of capsaicin over pregabalin in treating allodynia in peripheral neuropathic pain (18).

Chronic Neuropathic Pain After Breast Surgery for Breast Cancer

Chronic Postsurgical Neuropathic Pain: A Frequent Symptom

The prevalence of chronic pain after breast cancer is estimated at 47% in a study by Gartner involving 3,254 patients in Denmark in 2009 (19). Other studies have assessed the incidence of chronic neuropathic pain after breast surgery, but most lack sufficient power for generalization to all breast cancer patients.

Risk Factors for Chronic Neuropathic Pain After Breast Cancer Surgery

Several risk factors for chronicization have been identified in the literature. Among them, younger age—≤49 years in Mejdahl's Danish study (12) and 18–39 years in Gartner's study (19)—is associated with higher risk. Breast cancer in younger patients is often more aggressive, warranting more intensive treatments (19, 20). Conversely, age >70 years appears protective and is associated with fewer chronic postsurgical pain symptoms (21).

Axillary lymph node dissection is the second unanimously recognized risk factor, due to the risk of intercostobrachial nerve injury. According to Gartner, the risk of developing neuropathic pain is higher after axillary dissection than after sentinel lymph node biopsy (19). Additional risk factors include adjuvant chemotherapy, adjuvant radiotherapy, and preexisting chronic pain conditions such as chronic low back pain, osteoarthritis, or fibromyalgia (19, 20).

The presence of early neuropathic pain symptoms is also a predictor of chronic neuropathic pain (22). Finally, depression, psychological vulnerability, and stress are the psychological factors most strongly associated with chronic postsurgical pain (23).

Consequences of Pain Chronicization

Moderate-to-severe neuropathic pain correlates strongly with reduced quality of life (24). Although no specific studies have evaluated the economic impact of chronic pain after breast surgery, reduced quality of life is a key driver of the overall financial burden of breast cancer (25, 26).

Importance of Early and Appropriate Management

Early diagnosis, assessment, and management of neuropathic pain are essential to prevent chronicization, improve the quality of life of breast cancer surgery patients, and facilitate faster return to work. Early neuropathic pain management may also reduce societal costs, particularly for national health insurance systems.

References

1. HAS. Synthèse d'avis de la commission de transparence – QUTENZA (capsaïcine, antalgique local en patch. http://www.has-santefr/portail/upload/docs/application/pdf/2011-04/synthese_davis_qutenza_-_ct-8291pdf 2011.

If non-inferiority is demonstrated: to compare the efficacy of an early management strategy using 8% capsaicin topical treatment with that of standard oral pregabalin therapy on the evolution of ICBN after 2 months of treatment in patients who have undergone surgical excision for breast cancer.	The 11-point Numerical Rating Scale (NRS) for pain is collected at randomization (T0) and at Month 2 (T2) (see primary endpoint).	2 months
To compare the efficacy of an early management strategy using 8% capsaicin topical treatment (experimental arm) versus standard pregabalin therapy (control arm) on the evolution of ICBN after 6 months of treatment in patients who have undergone surgical excision for breast cancer.	The 11-point Numerical Rating Scale for pain is also collected at Month 6 (T6).	6 months
To compare patient-reported functional changes (activities, symptoms, emotions,	The PGIC, QLQ-C30, QLQ-BR23, and EQ-5D questionnaires are administered at T0, T2, and	6 months

and quality of life) between the two arms after 2 and 6 months of treatment.	T6 to assess functional changes and patient-reported quality-of-life outcomes in both treatment arms.	
To compare the reduction of the painful area between the two arms after 2 and 6 months of treatment.	The painful area is measured using pain mapping at baseline (T0), and after 2 months (T2) and 6 months (T6) of treatment. The surface area corresponds to the zone enclosed within the drawn boundaries of the painful region (centralized review).	2 months
To assess the safety profile of each treatment by collecting adverse events in each study arm.	Treatment tolerability will be assessed based on the number of patients experiencing at least one adverse event of grade ≥ 2 according to CTCAE v5.	6 months
To compare weight change between the two arms after 6 months of treatment.	Weight is collected at T0, T2, and T6.	6 months
In the capsaicin arm only, to estimate the proportion of patients for whom a single application was sufficient.	In the capsaicin arm, the number of applications and the total number of patches received by each patient during the 6-month period will also be recorded.	6 months
To assess the impact of anxiety and depression on treatment response for ICBN after breast cancer surgery.	The HADS questionnaire is collected at baseline, T2, and T6.	6 months
To evaluate the impact of pain duration prior to treatment initiation on therapeutic response.	Treatment effect will be assessed at 2 and 6 months using the 11-point NRS in both arms. Pain duration prior to initiation of treatment is self-reported, expressed in months, and collected at baseline	6 months
INCLUSION CRITERIA	
 1) Male or female patient who has undergone first-line surgical treatment for breast cancer, regardless of the type of surgery. 2) Age ≥ 18 years. 3) Healthy and non-irritated skin over the painful areas to be treated. 4) Neuropathic pain of the breast and/or axillary region consistent with intercostobrachial neuralgia, with a DN4 score ≥ 4, diagnosed between 3 and 12 months after surgery. 5) Written informed consent obtained and signed by the patient. 6) Adult patient covered by a national health insurance scheme. 	
NON-INCLUSION CRITERIA	
 1) Specific contraindications to the study treatments: 
 a. Pregabalin: hypersensitivity to the active substance or any excipient. b. Capsaicin: hypersensitivity to the active substance or any excipient. 2) Patient with diabetes. 3) Prior treatment with capsaicin or pregabalin between surgery and study inclusion. 4) Ongoing opioid treatment > 80 mg/day of morphine or equivalent at the time of inclusion. 5) Topical pain treatment within 7 days prior to inclusion. 6) Uncontrolled hypertension (systolic blood pressure ≥ 180 mmHg or diastolic blood pressure ≥ 90 mmHg) or recent history of cardiovascular events (stroke, myocardial infarction, pulmonary embolism). 7) Patient with chronic kidney failure. 8) Pregnant or breastfeeding women, or women who may become pregnant. 	

- 9) Individuals deprived of liberty or under legal protection (including guardianship or curatorship).
10) Inability to comply with the study's medical follow-up.

E) INVESTIGATIONAL TREATMENT DESCRIPTION

Active Ingredient (INN)	Brand Name	Pharmaceutical Form	Route of Administration	Dose per Administration
Capsaicin	QUTENZA	Cutaneous patches	Topical	640 micrograms of capsaicin per cm ² Patch size: 280 cm ²
Pregabalin	LYRICA	Capsule	Oral	50 mg to 600 mg

Therapeutic schema

The screening period extends from 3 months before surgery to 12 months after breast cancer surgery. Patients who agree to participate are scheduled for a screening visit between 3 and 12 months post-surgery. If they present with ICBN, defined by a DN4 score ≥ 4 , they will be included and randomized to receive either pregabalin (standard treatment) or topical capsaicin patch (experimental treatment), both of which are indicated for the management of peripheral neuropathic pain.

Pregabalin will be initiated with a gradual titration to reach a dose of 600 mg/day in two divided doses, depending on patient tolerability.

Capsaicin patches will be applied in a hospital setting to the painful area for 1 hour, with applications scheduled every 90 days.

All patients will undergo assessments at T0 (± 7 days) and T6 (± 7 days) regarding pain evolution (intensity and area), treatment tolerability, and quality of life.

The end of treatment and study follow-up is planned at the final pain-evaluation visit (T6).

F) STATISTICAL CONSIDERATIONS

SAMPLE SIZE DETERMINATION	
Statistical analyses will be performed using R software.
 
A total of 772 patients will be included, allocated into two balanced groups.
 
Sample size calculation
 
An interim analysis is planned once 300 patients have been included (minimum 150 per arm), based on the primary endpoint.
 
Alpha allocation:
 
 - 0.005 for the interim analysis - 0.045 for the final analysis 
Assumptions for calculating the required sample size:
 
 - At baseline, the standard deviation of NRS pain score is estimated at 2.0. - The expected mean difference in NRS (Capsaicin – Pregabalin) is 0. - The non-inferiority margin is set at +0.4 points on the NRS. - One-sided alpha risk: 4.5%. - Statistical power: 80%. 
Under these assumptions, 322 patients per arm are required (644 total). Considering a 20% rate of non-evaluable patients at 6 months, the total required sample size is 772 patients (386 per arm).

----------------------------------	---

DESCRIPTION OF ANALYSIS SETS	
Description of planned statistical methods
 
A descriptive analysis of the study sample will be performed. Data will be presented as follows:
 
 • Qualitative variables: expressed as percentages. • Quantitative variables: expressed as mean and standard deviation, or median and range, depending on the distribution. 
Comparisons will be performed as follows:
 
 • Qualitative variables: using the Chi-square test or Fisher's exact test when appropriate. 
Quantitative variables: using Student's t-test or a non-parametric test (Wilcoxon test) depending on distribution and normality assumptions.
 
Definition of Analysis Populations
 
 • The ITT population includes all randomized patients in the CAPTRANE study. Patients are analyzed according to the treatment arm to which they were randomized, regardless of the treatment actually received. • Modified Intention-to-Treat Population (mITT) • The mITT population includes all randomized patients who received at least one administration of study treatment; i.e., excluding patients withdrawn prematurely or incorrectly included before receiving treatment. Patients are analyzed according to their allocated arm, regardless of treatment actually received. • Per-Protocol Population (PP) • The PP population includes all randomized patients who received the allocated treatment according to the protocol. Patients who received any treatment other than that assigned are excluded from the analysis. • If non-inferiority is demonstrated at the pre-specified 0.4 threshold (primary endpoint in the PP population), a Student's t-test will be used to compare the mean 24-hour maximum NRS pain scores at T2 (2 months after randomization) between the capsaicin and pregabalin arms, in the mITT population. • Mean 24-hour NRS scores at T6 will be compared between arms using a Student's t-test. • The percentage of patients with at least a "notable improvement" (PGIC score ≥ 5) will be compared between arms using a Chi-square test. • Reduction in painful area will be expressed as a percentage relative to baseline. • Differences in painful area between T2–T0 and T6–T2 will be compared using a Student's t-test. • All grade ≥ 2 adverse events will be described by category and by treatment arm. • The number of patients experiencing at least one grade ≥ 2 toxicity event will be compared using a Chi-square test. • The percentage of patients with $\geq 5\%$ weight gain will be compared between arms using a Chi-square test. • A subgroup analysis of NRS pain scores at T2 and T6 will be performed among patients with probable anxiety disorder and those with probable depressive disorder according to baseline HADS scores. • A multivariable linear regression model will be used to estimate the impact of pain duration before inclusion (expressed in months) on pain intensity at T2 and T6 (NRS), adjusted for:
------------------------------	---

	
 - baseline NRS pain score, - treatment arm. 
Statistical stopping rules
 
An interim analysis will be conducted after inclusion of 150 patients per arm based on the primary endpoint (NRS at T6).
 
If a statistically significant difference in efficacy is observed at $\alpha = 0.005$, the study will be stopped for efficacy, regardless of which treatment demonstrates superiority.
 
Handling of missing, unused, or invalid data
 
Missing data for the numerical pain scale (NRS), painful area, and PGIC will not be imputed.
 
The proportion of missing data will be compared between arms using a Chi-square test.
 
Baseline characteristics of patients with missing data will also be compared.
 
Missing data for quality-of-life questionnaires (QLQ-C30, QLQ-BR23, EQ-5D) may be imputed according to EORTC manual recommendations.
 
Management of amendments to the analysis plan
 
Modifications to the statistical analysis plan may be proposed by the data monitoring committee (interim analysis, statistical tests, adverse event review, secondary objectives) if justified by emerging literature.
 
Protocol deviations will be identified and quantified.
 
Randomisation
 
Patients with a positive DN4 score will be randomized directly through the eCRF to be allocated to one of the following treatment arms:
 
 - Arm A (experimental): CAPSAICIN (patch), application of capsaicin patches to the painful area for 1 hour, with applications repeated every 3 months. - Arm B (standard): PREGABALIN (oral), oral pregabalin with progressive dose escalation. 
Validation of the randomization will automatically generate a confirmation email specifying the treatment arm allocated to the patient.
 
Randomization will be performed using balanced block allocation, stratified according to the following factors:
 
 - Study center - Pain intensity on the numerical rating scale (≥ 5) - Age (≥ 65 years) - HADS score (Incomplete, ≤ 18, > 18) - Pain duration (< 3 months or ≥ 3 months)
--	---

G) STUDY CALENDAR

DURATION OF INCLUSION PERIOD	36 months
TREATMENT DURATION	6 months
POST TREATMENT FOLLOW UP	6 months
STUDY COMPLETION DURATION (INCLUDING FU PERIOD)	42 months

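### QLQ-C30, QLQ-BR23 and EQ-5D fall at most under a generic two-sample test; a T0-adjusted comparison of named scales at T2 and T6 would be more precise with data already planned

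*Combined protocol and SAP*

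**What the plan says.** The objective, in section C (Secondary objectives and endpoints), reads "To compare patient-reported functional changes (activities, symptoms, emotions", "and quality of life) between the two arms after 2 and 6 months of treatment". Its instruments are given as "The PGIC, QLQ-C30, QLQ-BR23, and EQ-5D questionnaires are administered at T0, T2, and" "T6 to assess functional changes and patient-reported quality-of-life outcomes in both treatment arms". The evaluation-time column for this row shows 6 months only.

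Section F (Statistical considerations) touches these instruments in three places:

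- **Endpoint list.** The percentage of patients with a notable improvement ("PGIC score ≥ 5) will be compared between arms using a Chi-square test"). No visit is stated. QLQ-C30, QLQ-BR23 and EQ-5D are not in this list.
- **General comparison rule**, ahead of the list: "Quantitative variables: using Student's t-test or a non-parametric test (Wilcoxon test) depending on distribution and normality assumptions". No endpoint is named.
- **Missing data**: "Missing data for quality-of-life questionnaires (QLQ-C30, QLQ-BR23, EQ-5D) may be imputed according to EORTC manual recommendations". This is the only place in section F where the three questionnaires are named.

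Section E (Therapeutic schema) places the assessments that include quality of life at T0 and T6, without T2.

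**The concern.** Three of the four instruments assigned to this objective have no analysis of their own. The other comparative secondary objectives do: NRS at T2 and T6, painful area, grade ≥ 2 events, weight, the HADS subgroups and pain duration. Painful area is analysed as differences between visits, and the pain-duration regression adjusts for baseline NRS. So the plan uses change or baseline adjustment elsewhere, but not here.

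Two things are at stake. One is precision: T0 scores are collected, but the only rule that could apply does not use them as a covariate. The other is that the reported result is left open. Scale, visit, population and form of score (raw or change) could all be settled after the data are seen, in an open-label trial with patient-reported outcomes. The PGIC responder percentage does not fill the gap, because one dichotomised global rating cannot separate activities, symptoms, emotions and quality of life.

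**Working it through.** **1. Instruments traced from objective to analysis**

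| Instrument | Visits (section C) | Own analysis line (section F) | Otherwise covered by |
|---|---|---|---|
| PGIC | T0, T2, T6 | Score ≥ 5, Chi-square, no visit | – |
| QLQ-C30 | T0, T2, T6 | None | General t-test/Wilcoxon rule; imputation rule |
| QLQ-BR23 | T0, T2, T6 | None | Same |
| EQ-5D | T0, T2, T6 | None | Same |

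**2. The plan's own figure.** The documents give no sample size or power for the questionnaires. The 322 per arm used below is the evaluable number for the primary endpoint (section F: SD 2.0, margin 0.4, expected difference 0, one-sided 4.5%, power 80%). It reproduces: n = 2 × 2.0² × (1.695 + 0.842)² / 0.4² = 321.8, rounded up to 322.

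**3. Variance of the between-arm difference.** Assume equal SD at T0 and follow-up, with correlation r between them. The documents do not give r; 0.5 to 0.7 is an assumed range. Taking the raw follow-up score as 1:

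- change from T0: 2(1 − r)
- T0-adjusted: 1 − r²
- adjusted relative to change: (1 − r²) / [2(1 − r)] = (1 + r)/2

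| r | Change score | T0-adjusted | Cut against raw (r²) | Cut against change |
|---|---|---|---|---|
| 0.5 | 1.00 | 0.75 | 25% | 1 − 0.75 = 25% |
| 0.7 | 0.60 | 0.51 | 49% | 1 − 0.85 = 15% |

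At r = 0.7, 51% of the raw-score variance remains, so the cut is 49%.

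**4. Power, as an illustration.** Assumed: true difference 0.2 SD and two-sided 5%; 322 per arm is carried over from the primary endpoint. With V the relative variance from step 3, power = Φ(0.2 / √(2V/322) − 1.96).

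- Raw, V = 1: Φ(2.538 − 1.96) = 72%
- Adjusted, r = 0.5, V = 0.75: Φ(2.930 − 1.96) = 83%
- Adjusted, r = 0.7, V = 0.51: Φ(3.554 − 1.96) = 94%
- Change score: 72% at r = 0.5 (V = 1.00) and 91% at r = 0.7 (V = 0.60)

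**5. Number of comparisons.** Four domains plus EQ-5D at two visits gives 5 × 2 = 10 comparisons. If they were independent and each tested at 5%, the chance of at least one false positive would be 1 − 0.95¹⁰ = 40%. Independence is an assumption; scales from the same patients will be correlated.

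**The case against.** The strongest reply is that the plan does provide a test. The general rule applies to quantitative variables, and questionnaire scores are quantitative. The PGIC comparison is itself a between-arm result under this objective. This stands. A reader might infer from the endpoint list that the plan gives no between-arm result on patient-reported function or quality of life; the documents do not support that.

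A reader might also infer that a test on follow-up scores answers a different question from the objective, which speaks of change. That does not hold either. Under randomisation the expected T0 mean is the same in both arms, so the difference in follow-up scores and the difference in change from T0 estimate the same effect. Only precision differs. Nor does the general rule say that raw scores would be used; change scores are an equally possible reading, which is why both are compared above.

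It can also be said that the power figures show the benefit of covariate adjustment in general and rest on assumed inputs. That is fair: they illustrate size and measure nothing in this trial. A mixed model may also look like a preference in a plan built mainly on t-tests; ANCOVA at each visit serves the same purpose.

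What the reply does not meet is that the general rule names no scale, visit, form of score or population, and that adjustment has lower variance than either form of unadjusted test across the assumed range.

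**Conclusion.** The point holds as a free improvement to a secondary analysis. Only the PGIC has an endpoint-specific analysis, and its visit is not stated. QLQ-C30, QLQ-BR23 and EQ-5D fall at most under a generic test that is unbiased but makes no use of T0 as a covariate.

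The size depends on the T0-to-follow-up correlation, which the documents do not give. Over the assumed range, the gain is largest against raw scores and modest against change scores at the upper end (15%). The 0.2 SD difference and the two-sided 5% level are also assumptions. The primary non-inferiority result and the sample size are unaffected, so this is a change that should be made, not one on which the trial's main conclusion depends.

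**What to change.** In the planned analyses of section F:

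1. Replace the generic test for these questionnaires with a T0-adjusted comparison of arms: ANCOVA at each visit, or a linear mixed model on T2 and T6 scores with T0 score, arm, visit and arm-by-visit. Report the difference and 95% CI at T2 and at T6.
2. Apply it to one pre-named QLQ-C30 or QLQ-BR23 scale for each domain in the objective, and to EQ-5D. Summarise the remaining scales descriptively by arm.
3. State which of the defined populations (ITT, mITT or PP) is used.
4. Label these comparisons exploratory, or specify a multiplicity adjustment.
5. State the visit or visits at which the PGIC responder percentage is tested.
6. Reconcile section E (quality of life at T0 and T6) with section C (T0, T2 and T6), and the 6-month evaluation-time entry with an objective that names 2 and 6 months.

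The cost is a few lines of SAP text and a little analysis work. No extra patients are needed, and no extra data or visits provided the section C schedule is the one being followed.

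### The safety objective has no grade limit, but every planned adverse-event analysis starts at CTCAE grade 2, so most of the mild patch reactions the protocol expects would not be reported

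*Combined protocol and SAP*

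**What the plan says.** Section C, table of secondary objectives and endpoints, gives the safety objective as "To assess the safety profile of each treatment by collecting adverse events in each study arm". No grade restriction is attached to that collection. The endpoint beside it is restricted: "Treatment tolerability will be assessed based on the number of patients experiencing at least one adverse event of grade ≥ 2 according to CTCAE v5", evaluated at 6 months.

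Section F, list of planned analyses, has two adverse-event items:
- a description: "All grade ≥ 2 adverse events will be described by category and by treatment arm";
- a comparison: "The number of patients experiencing at least one grade ≥ 2 toxicity event will be compared using a Chi-square test".

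No any-grade summary, grade 1 summary or application-site summary is listed.

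Section B, in the paragraph on the 8% capsaicin patch, says that the product has a "low rate of adverse effects (10%), mostly mild erythema, burning sensations, or pruritus at the application site" and presents this as its main advantage.

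**The concern.** The objective is wider than every analysis that serves it. A threshold of grade 2 is a reasonable choice for a test of clinically relevant harm. The descriptive table has a different job: it is where a reader would look for a safety profile, and it stops at the same threshold. By the protocol's own account, most of what the patch is expected to cause lies at the mild end.

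This matters more than usual for two reasons. First, the primary hypothesis is non-inferiority on pain, with an expected difference of 0. If that is what the trial finds, tolerability will carry much of the argument for choosing one treatment over the other. Second, the trial is open-label. The judgement between grade 1 and grade 2 is made with treatment known, and under the plan it decides whether an event is reported at all. An all-grade table would show whether a difference at grade ≥ 2 reflects how often events occur or how they were graded.

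**Working it through.** **Scope of each element**

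| Element | Place | Grade range |
|---|---|---|
| Objective (collection of adverse events) | Section C | no limit stated |
| Endpoint | Section C | grade ≥ 2 |
| Description by category and arm | Section F | grade ≥ 2 |
| Chi-square comparison | Section F | grade ≥ 2 |
| Expected capsaicin effects | Section B | 10%, mostly mild |

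The floor enters at the endpoint and carries through both analyses.

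**The plan's own figure**

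The safety endpoint has no stated size or power, so the only figure to reproduce is the number of patients.
- Per arm for non-inferiority: n = 2σ²(z₀.₉₅₅ + z₀.₈₀)²/δ² = 2 × 2.0² × (1.695 + 0.842)²/0.4² ≈ 322. This matches section F.
- With the plan's 20% allowance: 322 × 1.2 = 386.4, stated as 386.

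**How many capsaicin patients the floor would leave out**

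Inputs from the documents: 386 patients per arm and a 10% adverse-effect rate. Assumptions:
- mild means CTCAE grade 1;
- the 10% counts patients, not events;
- a share m of affected patients have only mild events. The protocol says only that most effects are mild, so m is varied from 50% to 90%.

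Patients affected: 386 × 0.10 = 38.6. Left out: 38.6 × m. Counted: 38.6 × (1 − m). Visible rate: 10% × (1 − m).

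| m | Left out | Counted at grade ≥ 2 | Visible rate |
|---|---|---|---|
| 50% | 19.3 | 19.3 | 5% |
| 70% | 27.0 | 11.6 | 3% |
| 90% | 34.7 | 3.9 | 1% |

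With 322 evaluable patients instead of 386, 32.2 are affected and 16.1 (m = 50%) to 29.0 (m = 90%) are left out. An any-grade table would show all of them.

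**Can the direction of any distortion be worked out?**

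That needs an overall pregabalin rate and its mild share. The documents give neither; the only pregabalin rate is 3.5% for weight gain at 600 mg/day. Two invented scenarios show how far the answer depends on them:
- Both arms at 10% any grade, mild share 50% for pregabalin and 70% for capsaicin. Grade ≥ 2 rates are 10% × 0.5 = 5% and 10% × 0.3 = 3%. The floor makes capsaicin look better although equal numbers are affected.
- Pregabalin at 30% any grade with 90% mild, capsaicin at 10% with 70% mild. Grade ≥ 2 rates are 30% × 0.1 = 3% and 10% × 0.3 = 3%. The floor hides a threefold difference in favour of capsaicin.

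Both are arithmetically sound, and neither is supported by the documents.

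**The case against.** The strongest case on the other side is that this is a reporting preference. Grade ≥ 2 is a defensible threshold and applies identically to both arms. If patch reactions are mild and pregabalin's effects are more severe, a lower grade ≥ 2 rate for capsaicin is a true finding. Patient-reported symptoms are also covered by the QLQ-C30, QLQ-BR23 and EQ-5D, and tolerability is not the patch's only possible advantage: superiority on pain, pain at month 6, PGIC and painful area are all examined. Nothing here affects the primary result.

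Most of that stands, and it limits the point to the missing all-grade description. It does not remove the point. Quality-of-life scores are no substitute for a list of adverse events by category, and a stated objective to assess the safety profile is not met by tables that stop at grade 2.

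The size also rests on a reading of background prose. The documents do not map mild to a CTCAE grade, the word may qualify only the erythema, and the 10% is not said to count patients.

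Three stronger readings are tempting and are not supported:
- *Grade 1 events will not be collected.* The floor is stated for the endpoint and the analyses. The objective collects adverse events without a grade limit, and the document contains no eCRF specification from which non-recording could be inferred.
- *The floor biases the comparison towards capsaicin.* Mild pregabalin effects are excluded too, and without a pregabalin rate the direction is unknown. A probability of a spurious advantage can be calculated only from invented inputs.
- *The separate analysis of weight gain of at least 5% shows uneven handling of the arms.* Weight change is a secondary objective in its own right and is compared in both arms.

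**Conclusion.** The point holds as a gap between a stated objective and the analyses that serve it. Followed as written, the plan would leave most of the patch reactions it expects out of every adverse-event analysis: about 19 to 35 of some 39 affected capsaicin patients, conditional on the three assumptions set out in the working. Mild pregabalin effects, in a number that cannot be estimated, are omitted as well. The documents establish no bias between arms and no fault in the grade ≥ 2 test. Severity is minor: the primary conclusion, sample size and error rates are untouched, and the correction is a cheap improvement.

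**What to change.** Keep the grade ≥ 2 chi-square comparison. Then:
- in section F, replace the grade ≥ 2 description with one covering all grades (any grade, grade 1, grade ≥ 2) by category and arm, with a separate line for application-site reactions;
- beside the grade ≥ 2 result, report the difference between arms in the proportion of patients with an adverse event of any grade, with its 95% confidence interval;
- in section C, align the endpoint text with these analyses;
- confirm that grade 1 events are recorded in the eCRF in both arms.

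The cost is protocol and SAP wording, a few more tables and, if grade 1 events are not already entered, some additional data entry. Reported tolerability will look less favourable once mild events are counted.
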